3.2 INCLUSION CRITERIA

Patient:

- 1. Clinical signs and symptoms consistent with acute PE with duration of 14 days or less
- 2. Patients who present with CT confirmed PE
- 3. Defined as intermediate or high-risk PE (as defined within the ESC Guidelines¹)
- 4. Date of CT imaging within the two-year study period.
- 5. Patient is ≥ 18 years of age
- 6. Informed consent obtained
- 7. Evidence of cardiac dysfunction (Either biochemical or imaging features of RHS)

Operator:

1. Operator experience treating a minimum of 2 previous PE's and experience with Penumbra indigo systems (defined as 3 cases).

3.3 EXCLUSION CRITERIA

- 1. Known serious, uncontrolled sensitivity to radiographic agents
- 2. CT not available to evaluate PE
- 3. Low risk PE as defined by ESC guidelines¹
- 4. Current participation in another investigational drug or device study that may confound the results of this study. Studies requiring extended follow-up for products that were investigational but have since become commercially available are not considered investigational studies.
- 5. Other medical, social, or psychological conditions that, in the opinion of the Investigator, precludes the patient from appropriate consent, could limit the patient's ability to participate in the study.

4 STUDY DESIGN, PROCEDURES AND INTERVENTIONS

4.1 STUDY DESIGN

We estimate that each centre will see around 130 eligible patients per year and perform approximately 13 thrombectomies per year (4). Therefore, across the 12 centres we expect to see around 3000 eligible patients and around 300 thrombectomy patients across the two years. We expect around 70% of patients to consent to take part in the study due to its observational nature and therefore we expect between 2000 of PERT referred patients and 200 thrombectomy patients across the two years.

4.2 RECRUITMENT

Patients will be assessed for inclusion into the study by the research nursing team or trained member of the PERT team at point of referral to the local PERT team. Consent for inclusion in the data recording can be sought retrospectively in an out of hours setting, up to 96 hours post referral. All patients referred with an intermediate or high-risk PE (according to ESC guidelines (1)) will be included (after consent) into the wider dataset, with more specific data collected on those undergoing CAVT treatment.

4.3 CONSENT

Consent for inclusion into the trial dataset will be obtained by the research nurse or PERT team, only after a full explanation has been given, an information leaflet offered, and time allowed for consideration. Consent can be sought up to 96 hours after the referral to the PERT to allow for out of hours setting. No study specific data will be collected before a consent form is signed. The right of the participant to refuse to participate without giving reasons must be respected. There will be no change in the patients' treatment pathway. Patients will be able to withdraw from the study at any point. If a patient loses capacity, no further information will be obtained but their data already included will not be deleted. Patients who are unable to consent will be able to be included if a appropriate proxy consent is available. Patients who die within the 96 hours will also be able to be included if appropriate proxy consent available.

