2 STUDY OBJECTIVES

2.1 PRIMARY OBJECTIVES

- 1. To evaluate the effectiveness of PE CAVT as a treatment for intermediate and high-risk PE as measured by change pulmonary arterial pressure and in RV/LV (Right Ventricle to Left Ventricle diameter) ratio at 48 (- 24 / + 48) hours post procedure.
- 2. Ascertain the mortality and morbidity profile for CAVT within intermediate and high-risk PE, within 48 (± 12) hours post procedure, 30 (± 7) days, 90 (± 14) days and 6 months (+/- 30 days).

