2.2 OUTCOMES

Effectiveness of CAVT will be determined by the change in RV/LV ratio on Echocardiography and the reduction in direct invasive measurement of the Pulmonary artery pressure at the beginning and end of the procedure.

Technical success will be determined by the operator comparing pre and post imaging and pulmonary artery pressures. Morbidity and mortality will be expressed as percentage of the cohort. Imaging features, service design, PERT team decision and comorbidities effect on outcomes will be assessed via regression analysis.

The service design and effect on thrombectomy will be assess by service questionnaire at site set up describing the service design factors. Patient reported outcomes like quality of life and breathlessness will be assessed to determine improvement as per their validated questionnaires.

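### Section 4.3 stops all data collection, including vital status, when a consented participant loses capacity, so later deaths under primary objective 2 go unrecorded

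*Protocol*

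**What the plan says.** Section 4.3 of the protocol covers three situations in one paragraph.

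- Capacity lost after entry: "If a patient loses capacity, no further information will be obtained but their data already included will not be deleted".
- Capacity absent at entry: "Patients who are unable to consent will be able to be included if a appropriate proxy consent is available".
- Death before consent could be sought: "Patients who die within the 96 hours will also be able to be included if appropriate proxy consent available".

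The first rule has no exception for vital status and no proxy provision. The second and third rely on a proxy.

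Primary objective 2 in section 2.1 is to "Ascertain the mortality and morbidity profile for CAVT within intermediate and high-risk PE", at 48 hours, 30 days, 90 days and 6 months. Section 2.2 Outcomes adds that "Morbidity and mortality will be expressed as percentage of the cohort". Section 6.2 plans a survival analysis of factors affecting mortality. Section 5.2 collects relevant events from consent until the 6-month follow-up is complete, with no exception for lost capacity.

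On eligibility, exclusion 5 in section 3.3 removes patients with a condition that "in the opinion of the Investigator, precludes the patient from appropriate consent". Inclusion 6 in section 3.2 reads only "Informed consent obtained" and does not say by whom.

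**The concern.** Read literally, the stop rule blocks the discharge, 30-day, 90-day and 6-month mortality of anyone who loses capacity after consenting. It also blocks the day-2 echocardiogram if capacity goes before then. Loss of capacity is unlikely to be unrelated to outcome: Appendix 4 lists stroke and other neurological deficits, and cardio-respiratory arrest, among the expected serious events of the procedure, and these can remove capacity. Follow-up could therefore end because a morbidity event under primary objective 2 has occurred, and a death that follows would not be recorded.

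The rule also sits badly with the text around it. A patient who never had capacity can be followed to 6 months through a proxy, while one who agreed in person and later lost capacity cannot. Section 5.2 implies that collection continues. Twelve sites could resolve this differently, which matters for secondary objective 6, the comparison between hospitals.

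An analysis plan cannot repair this. The rule governs what may be collected, and vital status that was never obtained is not available to any later analysis.

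**Working it through.** **No stated figure to reproduce.** The protocol gives no mortality rate, no rate of capacity loss and no precision target for mortality. What follows illustrates size and direction on assumed inputs.

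**Inputs**

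- N = 200 CAVT patients (sections 4.1 and 6.1).
- q = share losing capacity after consent. Assumed: 3–8%, with 2–10% as a wider range.
- m1 = mortality after losing capacity. Assumed: 40–50%, with 20–40% as a milder range.
- m0 = mortality in everyone else. Assumed: 5%.

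**Formulas.** Deaths among those who lose capacity are taken to occur after the loss, and all others to be fully followed.

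- True mortality = (1 − q)·m0 + q·m1
- Reported, if these participants stay in the denominator with deaths unseen = (1 − q)·m0
- Reported, if they are dropped = m0
- Deaths unseen = N·q·m1

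**Results**

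| q | m1 | True | Reported, kept | Reported, dropped | Deaths unseen of 200 |
|---|---|---|---|---|---|
| 3% | 40% | 0.97×5% + 0.03×40% = 6.05% | 4.85% | 5% | 2.4 |
| 5% | 50% | 0.95×5% + 0.05×50% = 7.25% | 4.75% | 5% | 5.0 |
| 8% | 50% | 0.92×5% + 0.08×50% = 8.60% | 4.60% | 5% | 8.0 |
| 2% | 20% | 0.98×5% + 0.02×20% = 5.30% | 4.90% | 5% | 0.8 |
| 10% | 40% | 0.90×5% + 0.10×40% = 8.50% | 4.50% | 5% | 8.0 |
| 5% | 5% | 5.00% | 4.75% | 5% | 0.5 |

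For q of 3–8% with m1 of 40–50%, the relative shortfall with these participants kept is 1 − 4.85/6.05 = 20% to 1 − 4.60/8.60 = 47%. If they are dropped it is 1 − 5/6.05 = 17% to 1 − 5/8.60 = 42%.

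**Direction.** The last row separates the two mechanisms. If those who lose capacity die no more often than the rest, dropping them does no harm, but keeping them in the denominator with deaths unseen still lowers the estimate. If they die more often, both treatments understate mortality. In the survival model they would be censored at loss of capacity, and the usual assumption of non-informative censoring would probably fail.

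**Early deaths, a separate route.** Let e be the true share dying before consent and p the share of those deaths for which a proxy agrees. Survivors consent at the protocol's 70%. The observed share is e·p / (e·p + (1 − e)·0.70). At p = 0.70 this equals e. It is lower if p is below 0.70 and higher if p is above. The protocol gives no p, so the direction is open.

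**The case against.** The strongest counter-case has four parts.

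1. **A reader might infer that the sickest patients leave the mortality denominator.** The text does not say so. Data already held are kept and mortality is a percentage of the cohort, so what is lost is deaths from the numerator, or follow-up time by censoring. Only patients never enrolled are absent from the denominator. This corrects the mechanism but does not remove the downward direction.
2. **The rule may touch few patients.** Consent may be sought up to 96 hours after referral to allow for out-of-hours cases. A patient who is sedated, arrests or has a stroke before signing comes under proxy entry, not the stop rule. Section 5.2 may also pick up some deaths related to CAVT. Both points stand and limit the size, but section 5.2 can help only by overriding section 4.3.
3. **A reader might see exclusion 5 as a flat ban that contradicts proxy entry.** It is an investigator judgement about appropriate consent, and section 4.3 uses the parallel idea of an appropriate proxy. The two can be read together: exclude only where neither the patient nor a proxy can give consent. It is an ambiguity to clear up.
4. **A reader might add that requiring a proxy for early deaths biases mortality downward.** That holds only if proxies agree less often than the 70% expected of patients, which the documents do not show.

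**Conclusion.** The concern holds in a limited form. Section 4.3 contains an explicit rule that, if followed, leaves later deaths and morbidity unrecorded for participants who lose capacity after consenting. It is inconsistent with proxy entry in the same paragraph and with event collection to 6 months in section 5.2.

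Mortality under primary objective 2 is likely to be understated on either of two conditions: these participants die more often than others, or they stay in the denominator with deaths unseen. On the assumed inputs (3–8% lose capacity, 40–50% of them die, 5% of the rest die), true mortality of 6.1–8.6% would be reported as 4.6–4.9% with them kept or 5% with them dropped. That is about 2 to 8 unseen deaths in 200. With 2% losing capacity and 20% of them dying, the loss is under one death. None of these inputs comes from the protocol, so the figures show scale only.

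The documents do not support saying that the sickest are systematically removed from the cohort, or that early deaths bias the estimate in a known direction.

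**What to change.** 1. Replace the stop sentence in section 4.3. Subject to REC approval, when a participant loses capacity, proxy agreement is sought as at entry to continue collecting vital status, readmission and adverse events from the record; questionnaires stop. State whether the day-2 echocardiogram is covered.
2. Align section 5.2 with the new sentence, so that one rule governs collection to 6 months.
3. State that appropriate consent in exclusion 5 and consent in inclusion 6 include proxy consent under section 4.3. Carry the wording into the study summary and flow chart.
4. Report the number of participants who lost capacity.

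A log of deaths among patients who never consented should not be added as it stands, because section 4.3 also says "No study specific data will be collected before a consent form is signed". It would first have to be reconciled with that rule.

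The cost is protocol and REC wording plus some extra proxy contacts. No new assessments are needed. Whether continuation by proxy is permissible is for the REC; the documents do not settle it.

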4.4 STUDY ASSESSMENTS

Data will then be collected regarding admission information, imaging parameters, decisions to treat and how the patient was treated. Data will be collected by the research nursing team and will be maintained on anonymised electronic research specific (Dendrite) database.

Follow up

Follow up data, including 30 days, 90 days and 6-month outcomes will be assessed. The follow up with the questionnaires will be administered by the Dendrite platform.

Organisation

A short service-based questionnaire will be sent to each centre to establish centre-specific systems such as on call rota, PERT team activation, reporting practices and capture data around routine decision-making at that site. This will be completed by the site team at registration at each site and will take approximately 5 minutes to complete.

4.5 DEFINITION OF END OF STUDY

This is defined as the date of the last data submitted by the site. The sponsor will notify the REC, in writing, within 90 days of the end of the study.

Recruitment will be monitored with specific review at 1 year and 18 months. If recruitment at >120 thrombectomies at 1 year or >180 thrombectomies (i.e. greater than 20%) then the study will complete upon the final (200 thrombectomy) admission into the database unless an amendment to increase the specified end point is agreed with the sponsor, funder and with approval of the REC. In the event of under recruitment at 1 year or 18 months (<90 thrombectomies or <150 respectively then an extension or additional sites will be considered in conjunction with the sponsor, funder and with approval of the REC.

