Dendrite	Dendrite clinical systems, electronic research database
Section 251	The purpose of section 251 support is to give the data controller a legal means of providing access to confidential patient information without consent.
SOP	Standard Operating Procedure
SPSS	Statistical Product and Service Solutions (statistical software suite)
UHP	University Hospitals Plymouth NHS Trust
USS	UltraSound Scan
WBC	White Blood Cell

KEY WORDS:

Pulmonary embolism, Thrombectomy.

STUDY SUMMARY

Study Title TiPE

Study Design Prospective observational study to evaluate the use of Computer aided

vacuum thrombectomy (CAVT) within the context of intermediate and

high-risk PE.

Study Participants Patients presenting with intermediate or high-risk PE (as defined by

European Society of Cardiology (ESC) guidelines1) at one of the

participating hospitals.

Eligibility Criteria Study Site Criteria:

1. Availability of 16Fr Penumbra Flash

2. Operational PE Response team

3. Operator experience treating a minimum of 2 previous PE's and experience with Penumbra indigo systems (defined as 3 cases).

Inclusion Criteria Participants:

1. Clinical signs and symptoms consistent with acute PE with duration of 14 days or less

2. Patients who present with CT confirmed PE

3. Defined as intermediate or high-risk PE (according to ESC guidelines¹)

4. Date of CT imaging from within the two-year period

5. Patient is ≥ 18 years of age

6. Informed consent obtained

7. Evidence of cardiac dysfunction (Either biochemical or imaging features of RHS)

Exclusion Criteria:

- 1. Known serious, uncontrolled sensitivity to radiographic agents
- 2. CT not available to evaluate PE
- 3. Low Risk PE as defined by ESC guidelines¹
- 4. Current participation in another investigational drug or device study that may confound the results of this study. Studies requiring extended follow-up for products that were investigational but have since become commercially available are not considered investigational studies
- 5. Other medical, social, or psychological conditions that, in the opinion of the Investigator, precludes the patient from appropriate consent, could limit the patient's ability to participate in the study, including compliance with follow-up requirements, or that could impact the scientific integrity of the study

Planned Sample Size 2000 eligible patients and 200 thrombectomy patients

Follow-up Duration 6 months from date of PE or date of death, whichever is sooner

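### The fast-recruitment clause in section 4.5 is worded to end the study, not just recruitment, at the 200th thrombectomy, which contradicts the end-of-study definition and the 6-month follow-up

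*Protocol*

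**What the plan says.** Protocol section 4.5 first defines the end of study: "This is defined as the date of the last data submitted by the site". The next paragraph opens "Recruitment will be monitored with specific review at 1 year and 18 months" and gives the trigger for fast recruitment as "If recruitment at >120 thrombectomies at 1 year or >180 thrombectomies (i.e. greater than 20" (a percent sign follows). If the trigger is met, "the study will complete upon the final (200 thrombectomy) admission into the database". The only exception is "unless an amendment to increase the specified end point is agreed with the sponsor, funder and with approval of the REC". The paragraph does not mention follow-up.

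Elsewhere the protocol asks for 6 months of data without a fast-recruitment exception:

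- The study summary sets follow-up at "6 months from date of PE or date of death, whichever is sooner" and plans a study period of 30 months.
- Primary objective 2 (section 2.1) is to "Ascertain the mortality and morbidity profile for CAVT within intermediate and high-risk PE" at 48 hours, 30 days, 90 days and 6 months.
- Section 5.2 collects relevant events until 6 months after the index procedure.
- Section 7.2 and Appendix 1 schedule the 6-month assessment for all participants.

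**The concern.** One section gives two end points that cannot both hold. When the 200th thrombectomy patient enters the database, that patient's 90-day and 6-month data do not yet exist, so the last data cannot have been submitted. The subject of the clause is the study, not recruitment, and it stands under the heading that defines the end of study.

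Primary objective 2 is at stake. A literal reading would remove late follow-up from the most recently enrolled patients, in both the CAVT and the non-CAVT groups.

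There is also an operational consequence. The ethics committee must be notified within 90 days of the end of the study (section 4.5), and archiving follows the end-of-study declaration (section 7.5). Sites in a fast-recruiting study could not tell from the text whether follow-up and safety collection should continue after the 200th admission.

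**Working it through.** **Inputs.** Target of 200 CAVT patients (study summary: "2000 eligible patients and 200 thrombectomy patients"). Recruitment over two years (section 4.1). Triggers of more than 120 and more than 180 thrombectomies (section 4.5); the text does not attach a time to the 180, which is read here as the 18-month review. Follow-up of 6 months or death. Planned study period of 30 months.

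**Step 1: reproduce the triggers.** The planned rate is 200/24 = 8.33 per month, which gives 100 at 12 months and 150 at 18 months. Adding 20% gives 1.2 × 100 = 120 and 1.2 × 150 = 180, which match the protocol. Both equal 10 per month (120/12 and 180/18).

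**Step 2: shortfall at the trigger rate.** Assume uniform accrual at r per month. The number with less than f months of follow-up at the 200th admission is r × f. At r = 10 the 200th admission falls at 200/10 = month 20.

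| Time point | Number short | Share of 200 |
|---|---|---|
| 30 days (f = 1) | 10 × 1 = 10 | 5% |
| 90 days (f = 3) | 10 × 3 = 30 | 15% |
| 6 months (f = 6) | 10 × 6 = 60 | 30% |

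The protocol's ±30-day window at 6 months (f = 5 to 7) gives 50 to 70 patients, or 25% to 35%.

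**Step 3: other accrual patterns that meet a trigger.** The 6-month shortfall is the number admitted in the last 6 months before the 200th.

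| Pattern | Number short at 6 months | Share of 200 |
|---|---|---|
| 180 at 18 months, 200th at month 24 | 200 − 180 = 20 | 10% |
| 121 at 12 months, 200th at month 24 | (79/12) × 6 = 39.5 | about 20% |
| 121 at 12 months, then the planned 8.33 per month | 8.33 × 6 = 50 | 25% |
| Steady 10 per month | 60 | 30% |
| Steady 12.5 per month | 75 | 37.5% |
| Steady 15 per month | 90 | 45% |

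Deaths before the cut are ignored. Follow-up of those patients is already complete by definition, so counting them would lower the shares slightly.

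**Step 4: non-CAVT participants.** The trigger counts thrombectomies only, so the total affected depends on how overall enrolment behaves. If it speeds up in proportion, it is 100 per month and 100 × 6 = 600 of 2,000 participants would be short of 6 months. If it stays at plan, it is 2,000/24 = 83.3 per month, and 83.3 × 6 = 500 of about 1,667 enrolled by month 20 would be short. The protocol does not settle which applies.

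**Step 5: dates under the two readings, at 10 per month.** If the study ends at the 200th admission, it ends at month 20 and the ethics committee is notified by about month 23. If only recruitment closes, the last 6-month visit falls at month 20 + 6 = 26, or about 27 with the window. That is inside the planned 30 months, and the rule costs no patient any follow-up.

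**The case against.** The strongest reply is that the paragraph sets a recruitment cap. It opens with recruitment monitoring, its triggers are recruitment counts, its companion sentence deals with under-recruitment, and its exception concerns raising the target. The formal definition of end of study comes first in the same section. Every other section requires 6-month data, and 30 months is two years of recruitment plus six months of follow-up. Read as a cap, the sentence contradicts nothing. This stands as an account of what the authors probably meant. It does not cure the wording, because the clause names the study and says nothing that preserves follow-up.

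Three stronger readings might be inferred, and the documents do not support them:

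- **That the sponsor chose to truncate follow-up.** Nothing outside this clause suggests it, and the rest of the protocol points the other way.
- **That the last patient would not have even the 48-hour echocardiogram.** Consent may be taken up to 96 hours after referral, the echocardiogram window is day 2 (+2/−1 days), and the trigger is entry into the database, not into hospital. Entry could fall after the echocardiogram. The phrase could even mean completed data entry, which is a further ambiguity.
- **That 30% of CAVT patients, or 600 of 2,000 participants, is a firm figure.** The first assumes uniform accrual at exactly the trigger rate. The second also assumes that non-CAVT enrolment speeds up in step.

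**Conclusion.** The clause is wrong as worded and should be corrected. It conflicts with the end-of-study definition in its own section, with the 6-month follow-up and with primary objective 2. The defect lies in the wording of a contingency rule; it is not evidence of a plan to stop follow-up early, and no sample size or analysis is shown to be wrong.

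The loss arises only if recruitment passes a trigger and the clause is then applied literally. In that case about 30% of CAVT patients would lack 6-month follow-up under uniform accrual at 10 per month, with a range of roughly 10% to 45% over the accrual patterns examined. Recent non-CAVT participants would also be cut off, in a number that the protocol does not fix.

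**What to change.** Reword the fast-recruitment clause in section 4.5 along these lines: *recruitment will close on admission of the 200th consented thrombectomy patient, unless the sponsor, funder and REC agree an amendment to raise this number; all enrolled participants will be followed to 6 months or death, and the end of study remains the date of last data submitted.*

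The amendment exception should stay, since nothing is wrong with it. The cost is one sentence in the protocol. It adds no visits to those already planned.
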